#### 8.3.3. Confounders and effect modifiers

The study will examine the effect of the following potential confounders and effect modifiers on the risk for outcomes of interest.

#### **Demographic variables**

- Age
- Sex
- Route of HIV Infection
- Ethnic origin
- Geographic region
- Number of years since HIV diagnosis
- Date of ART initiation
- Date CAB+RPV LA started

#### Virologic variables at regimen initiation

- HIV VL at initiation of CAB+RPV LA regimen
  - o Categorical:
    - <50 copies/mL

    - Individuals with ≥50 copies/mL at regimen initiation should not be included in the study. copies/mL

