#### 8.2.2. Inclusion Criteria

The study population will consist of HIV positive male or female aged 18 years or over from NEAT ID Network clinical sites who are prescribed CAB+RPV LA regimen and:

- Virologically suppressed (HIV-1 RNA <50 copies/mL) at the time of regimen initiation.
- No evidence of prior virological failure with agents of the NNRTI and INI class
- No evidence of present or past documented viral resistance to, agents of the NNRTI and INI class

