#### Clinical variables at regimen initiation

- HIV Subtype
- History of previous use of integrase inhibitor-based or NNRTI-based regimen
- History of previous virological failure
- History of previous HIV drug resistance and any historical HIV-1 subtype information, where available
- Body Mass Index (BMI), height, weight
- History of AIDS-defining Events (ADE)
- Concurrent medications (Etravirine, Carbamazapine, Oxcarbazepine, Phenytoin, Phenobarbital, Rifampicin, Rifapentine, Rifabutin, Ethinyl estradiol and Levonorgestrel, Norethindrone, Ribavirin, Ketoconazole, Fluconazole, Itraconazole, Posaconazole, Voriconazole, Clarithromycin, Erythromycin, Dexamethasone, Methadone, Digoxin, Metformin, Paracetamol, Atorvastatin, Sildenafil, Vardenafil, Tadalafil)

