# Assessment of factors associated with non-adherence, virologic failure, discontinuation and resistance

Univariable and multivariable analyses will be performed to identify factors that probably modified the effect of the study treatment on the risk of outcomes of interest. Cox regression models will be used to assess the factors associated with virologic failure, with non-adherence and with the discontinuation of CAB+RPV LA regimen. Logistic regression will be used to assess factors associated with drug resistance among participants with virological failure, if the number of events allow this analysis. Variables with univariable P<0.20 will be retained for the multivariable analysis.

All variables described at section 8.3.3 will be assessed. We will assess whether continuous variables will be better modelled as continuous variables or as terciles based on the lowest value of Akaike's information criterion (AIC) for the corresponding univariable Cox regression models or univariable logistic regression models according to the outcome of interest, and grouped together the closest values in order to obtain two classes for certain variables.

Sensitivity Analysis: As some parameters with missing data can influence the outcome of interest, to quantify the potential effect, we will create 5 datasets in which missing data will be replaced using Rubin's multiple imputation method. Instead of filling in a single value for each missing value, multiple imputation procedure replaces each missing value with a set of plausible values that represent the uncertainty about the right value to impute. Analyses will be run on each of the 5 data sets, and the results will be combined with Rubin's rules. Pooling the multiple parameter estimates from the 5 datasets into one estimate along with its variance (which combines the conventional sampling variance and the extra variance caused by the missing data) will help understand the effect of the missing data.

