**HIV Medical History** 

ID	CODE	NAME	EXP.CODE	TYPE	FMT/LEN	DERIVATION	CAT. VALUES
1	ZORNID	Subject ID	PORTID	Text	10	See Appendix	
2	INC_VS	suppressed (HIV-1 RNA <50 copies /mL	INC_VS	Category	3		N=No Y=Yes
3	INC_VF	No evidence of prior virological failure with agen	INC_VF	Category	3		N=No Y=Yes
4	INC_VR	No evidence of present or past recorded viral resi	INC_VR	Category	3		N=No Y=Yes
5	CONREQ	Was patient consert required by local ethics appro	CONREQ	Category	3		N=No Y=Yes
6	CON	Was patient informed consent provided?	CON	Category	3		N=No Y=Yes
7	CONDAT	Consent Date	CONDAT	Date/Time	dd/mm/yyyy		
8	CONNAM	Name of Consenting Clinician	CONNAM	Text	100		
9	ICFVER	ICF Version Used	ICFVER	Text	10		
10	SUBINF	Confirm that the subject has been notified in writ	SUBINF	Category	3		Y=Yes
11	AGE	Age	AGE	Integer	#99		
12	SEX	Sex	SEX	Category	6		M=Male F=Female
13	INFRT	Route of HIV Infection	I INFRT	Text	100		
14	ETHNIC	Ethnicity	ETHNIC	Category	26		See Appendix

eForm Code: DEMOG eForm Title: Demographics and Consent - Layout
Is HIV diagnosis date known?  No Yes
HIV diagnosis date  DIAGDAT
If date not known, please estimate number of years since diagnosis
Date of ART initiation ARTINDAT
HIV Subtype
HIV Subtype Group (if known)
Has the subject previously used an integrase inhibitor-based or NNRTI-based regimen  O  No  Yes
For Office Use Only
Data Daview Dassas Baview Data Natas for New Daview

Data Review Reason	Review Date	Э	Notes for Next Review
CRREAS	 CRDAT		CRNOT

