# Regimen Initiation

Regimen Initiation
Date CAB+RPV LA regimen started LASTDAT
Viral Load at Regimen Initiation  Please record sample taken on day of initiation, if possible.  Otherwise, please record last sample taken prior to regimen initiation
Date of sample VLDAT
Viral Load Greater Than or Less Than
HIV RNA viral load VLOAD
CD4 Count at Regimen Initiation  Please record sample taken on day of initiation, if possible.  Otherwise, please record last sample taken prior to regimen initiation
Date of Sample CD4DAT
CD4 Count CD4 Count Unit CD4UNIT
CD4 nadir prior to initiation of CAB+RPV LA CD4NAD CD4NAD CD4NAD CD4NAD
Height and Weight at Regimen Initiation
Are height and weight available at regimen initiation?  No Yes
Height (cm) HCM
Weight (kg) WKG
Is the BMI known? O No Yes
BMI BMI (Derived)

ID	CODE	NAME	EXP.CODE	TYPE	FMT/LEN	DERIVATION	CAT. VALUES
1	ZORNID_D	Subject ID	20R1ID D	Text	10	BSL:DEMOG:SUBJID	
2	LASTDAT	Date CAB+RPV LA regimen started	LASTDAT	Date/Time	dd/mm/yyyy		
3	VLDAT	Date of sample	VLDAT	Date/Time	dd/mm/yyyy		
4	VLGL	Viral Load Equal To, Greater Than or Less Than		Category	1, Optional		0=< 1=> 2==
5	VLOAD	HIV RNA viral load	VLOAD	Integer	#####9		
6	CD4DAT	Date of Sample	CD4DAT	Date/Time	aa/mm/yyyy		
7	CD4COUNT	CD4 Count	CD4COUNT	Real	######9.9###		
8	CD4UNIT	CD4 Count Unit	CD4UNIT	Category	9		1=cells/uL 2=10^9/L 3=10^6/L 4=Cells/mm3 5=10^3/uL
9	CD4NAD	CD4 nadir prior to initiation of CAB+RPV LA	CD4NAD	Real	######9.9### ###		
10	CD4NADU	CD4 Nadir Unit	CD4NADU	Category	9		1=cells/uL 2=10^9/L 3=10^6/L 4=Cells/mm3 5=10^3/uL
11	HWAVAIL	Are height and weight available at regimen initiat		Category	3		N=No Y=Yes
12	HCM		HCM	Integer	#99		
13	WKG	Weight (kg)	WKG	Integer	#99		
14	BMIYN		BMIYN	Category	3		N=No Y=Yes
15	BMI		BMI	Integer	99		
16	BMI_D	BMI (Derived)	BMI_D	Integer	99	WKG/(HCM*HCM)	

Data Review Reason	Review Date	Notes for Next Review
CRREAS	CRDAT	CRNOT

eForm Code: INIT eForm Title: Regimen Initiation - Layout

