## **Antiretroviral Treatment**

#### Please record:

Previous regimens received in the year prior to initiation of CAB+RPV LA regimen Oral-bridging therapy or any other ARV regimen while on CAB+RPV LA regimen Regimen the subject switched to after discontinuation of CAB+RPV LA regimen

Regimen type		Drug Name	•				If Other Regimen,	Dose
							Please Specify	7
ANTREGTYP		ANTDRUG						ANTDOS
Unit	Frequency		If Other Frequency,	Start Date	Ongoing	End Date	ReasorPorStopping	If Other Reason,
	1		Please Specify					Please Specify
ANTUNIT	ANTFREQ			ANTSTDAT	ANTON	ANTENDAT	ANTSTREAS	
			ANTFREQOTH					ANTSTREASOTH

Please continue to record viral load and resistance test results in the Viral Load and Restsiance Testing eForms, using the links below

Viral Load

Resistance Testing

Data Review Reason	Review Date	)	Notes for Next Review
CRREAS	CRDAT		CRNOT

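### Section 8.3.3 gives baseline viral load a single possible category, and prior INSTI and NNRTI use are merged in one yes/no item, so class-specific exposure older than one year is lost

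*Protocol*

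**What the plan says.** The section 8.7 text on factors associated with non-adherence, virologic failure, discontinuation and resistance plans univariable and multivariable Cox and logistic models and states: "All variables described at section 8.3.3 will be assessed".

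**Viral load.** Section 8.3.3, under virologic variables at regimen initiation, lists viral load only in categorical form. The one level is below 50 copies/mL, followed by the note "Individuals with ≥50 copies/mL at regimen initiation should not be included in the study". The inclusion criterion in section 8.2.2 is the same condition: "Virologically suppressed (HIV-1 RNA <50 copies/mL) at the time of regimen initiation". The Regimen Initiation form in Annex 1 records more than this. It has a numeric field, "HIV RNA viral load VLOAD", and a qualifier field (VLGL), "Viral Load Equal To, Greater Than or Less Than", which is marked optional.

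**Prior class use.** Section 8.3.3, under clinical variables, has one item: "History of previous use of integrase inhibitor-based or NNRTI-based regimen". The Demographics and Consent form captures it as a single No/Yes field (PREVNN): "Has the subject previously used an integrase inhibitor-based or NNRTI-based regimen". The Antiretroviral Treatment form records drug names and dates, but for earlier treatment it asks only for "Previous regimens received in the year prior to initiation of CAB+RPV LA regimen".

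**Subtype.** The coded field labelled HIV Subtype offers HIV-1 and HIV-2. A free-text subtype group field follows it on both the demographics and the resistance testing forms.

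**The concern.** A factor analysis needs covariates that differ between participants and that match the question. As listed, viral load does not differ at all. The prior-use item does differ, but it answers whether someone has had either class. The regimen consists of one integrase inhibitor and one NNRTI, so the natural question is about each class separately.

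The two defects differ in how easily they can be repaired. The viral load value is in the database, so only its definition is wrong. Class-specific history older than one year is never collected, so no later analysis plan can restore it without a return to the medical records. Section 8.4 expects only 20 to 60 virologic failures, which leaves little room to lose covariate information.

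**Working it through.** The plan gives no figure on this point to reproduce. The check compares section 8.3.3 with the Annex 1 fields and then gives an illustrative size.

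**1. Viral load as listed.** For a binary covariate with prevalence p in a Cox model with D events, the information is D × p × (1 − p) × (ln HR)². With everyone below 50 copies/mL, p = 1 and p(1 − p) = 0. The information is 0 at D = 20 and at D = 60. The rule in section 8.7 for choosing between continuous and tercile forms does not clearly help: section 8.3.3 lists CD4 count as both continuous and categorical, but viral load only as categorical.

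**2. Viral load as recorded.** The numeric value with its qualifier can separate a result below the assay limit from a detected result under 50, where the laboratory reports it. If the optional qualifier is left blank, a result reported as <20, for example, would be stored as 20 and look like a measured value.

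**3. Prior class use, by what the forms reveal.**

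| Situation | Prior INSTI | Prior NNRTI |
|---|---|---|
| PREVNN = No | known: no | known: no |
| Yes, INSTI but no NNRTI in last year | known: yes | unknown before last year |
| Yes, NNRTI but no INSTI in last year | unknown before last year | known: yes |
| Yes, both in last year | known: yes | known: yes |
| Yes, neither in last year | at least one used, which one unknown | at least one used, which one unknown |

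So the gap is class-specific exposure older than one year among those answering Yes.

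**4. Illustrative size.** The documents give neither prevalences nor hazard ratios. Assume HR 2 for NNRTI use, no effect of INSTI use, independent use of the two classes, and PREVNN as the only source. Let a be NNRTI prevalence and b INSTI prevalence.

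- Share answering Yes: m = 1 − (1 − a)(1 − b)
- NNRTI share among Yes: q = a/m
- Apparent hazard ratio: H = (1 − q) + 2q
- Fraction of information kept: m(1 − m)(ln H)² ÷ [a(1 − a)(ln 2)²]

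| a / b | m | H | Merged item, per event | NNRTI item, per event | Kept |
|---|---|---|---|---|---|
| 30% / 80% | 0.86 | 1.349 | 0.1204 × 0.0895 = 0.0108 | 0.21 × 0.480 = 0.101 | 11% |
| 50% / 60% | 0.80 | 1.625 | 0.16 × 0.236 = 0.0377 | 0.25 × 0.480 = 0.120 | 31% |
| 50% / 30% | 0.65 | 1.769 | 0.2275 × 0.326 = 0.0741 | 0.25 × 0.480 = 0.120 | 62% |

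In the middle row, approximate power is Φ(√(D × information per event) − 1.96). With a separate NNRTI item and with the merged item respectively, it is 34% and 14% at 20 failures, 59% and 23% at 40, and 77% and 32% at 60. These figures ignore the Antiretroviral Treatment form and so overstate the loss.

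**The case against.** The strongest reply is that the data are richer than section 8.3.3 suggests. Viral load is stored as a number with a qualifier and a sample date, and a finer cut of a recorded value is often set in the analysis plan, which is not at hand. That stands as far as capture goes. A reader might infer that the study can say nothing about residual viraemia, and the documents do not support that. What remains is that the protocol itself lists a one-level variable and commits to assessing it.

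On prior use, the form matches the protocol item exactly, so this is a chosen composite and not a contradiction. The treatment form also shows the class of every regimen in the year before initiation. Both points are correct. A reader might infer that the two classes can never be told apart; in fact only older exposure is lost. The size is also uncertain: it rests on assumed prevalences and an assumed hazard ratio, and participants with evidence of prior failure on, or resistance to, either class are excluded, which makes a hazard ratio of 2 for exposure speculative.

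A reader might also infer that subtype is not collected. It is, in free text on two forms, and coding short text is routine data management. Only the label of the HIV-1/HIV-2 field is wrong.

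**Conclusion.** The point holds for two variables. Baseline viral load, as listed in section 8.3.3, is constant by the inclusion criterion, so the promised assessment cannot be done in that form. This follows from the text and needs no assumption. Class-specific INSTI and NNRTI exposure older than one year is not captured, and this is the more serious defect because analysis cannot repair it.

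The size of the second loss is not known from the documents. The 11% to 62% of information kept is illustrative: it assumes HR 2 for NNRTI use alone, independent use of the classes and no other source. The true loss is smaller because class use in the last year is recorded. Neither defect affects the main estimates of failure, discontinuation or resistance. They limit the factor analysis, and the changes are worth making because they are cheap.

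**What to change.** **(a) Viral load.** In section 8.3.3, replace the single class by two: below assay limit or not detected, versus detected and below 50 copies/mL. Derive them from VLOAD and VLGL, and make VLGL mandatory. The downside is that assay limits may differ between sites: a laboratory that reports only <50 would place every such result in the first class, so the reported limit should be checked by site.

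**(b) Prior class use.** Split PREVNN into prior INSTI (yes/no) and prior NNRTI (yes/no), split the section 8.3.3 item in the same way, and assess both. The cost is one extra yes/no item per participant. For anyone already entered, sites would have to return to the records.

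**(c) Minor.** Relabel the HIV-1/HIV-2 field as HIV type and take subtype from the free-text field HIVSUBGP, coded centrally.

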#### Immunologic variables at regimen initiation

- CD4 cell count at initiation of CAB+RPV LA regimen
  - Continuous (cells/μL)
  - o Categorical:
    - $CD4 \ge 500 \text{ cells/}\mu\text{L}$
    - CD4 count  $\geq$ 350 to <500 cells/ $\mu$ L
    - CD4 count <350 cells/µL

CD4 nadir prior to initiation of CAB+RPV LA

#### Clinical variables at regimen initiation

- HIV Subtype
- History of previous use of integrase inhibitor-based or NNRTI-based regimen
- History of previous virological failure
- History of previous HIV drug resistance and any historical HIV-1 subtype information, where available
- Body Mass Index (BMI), height, weight
- History of AIDS-defining Events (ADE)
- Concurrent medications (Etravirine, Carbamazapine, Oxcarbazepine, Phenytoin, Phenobarbital, Rifampicin, Rifapentine, Rifabutin, Ethinyl estradiol and Levonorgestrel, Norethindrone, Ribavirin, Ketoconazole, Fluconazole, Itraconazole, Posaconazole, Voriconazole, Clarithromycin, Erythromycin, Dexamethasone, Methadone, Digoxin, Metformin, Paracetamol, Atorvastatin, Sildenafil, Vardenafil, Tadalafil)

#### Comorbidities

- o HCV co-infection
- o HBV co-infection
- ESLD (hepatocellular carcinoma, ascites, hepatorenal syndrome, grade III/IV hepatic encephalopathy, unspecified liver decompensation, oesophageal variceal bleeding, spontaneous bacterial peritonitis, liver transplantation)
- CVD (myocardial infarction, stroke, invasive coronary procedure)
- o CKD (confirmed [>3 months apart] eGFR <60/ml/min/1.73m^2 in persons with eGFR at regimen initiation ≥60/ml/min/1.73m^2 and confirmed 25% decline in eGFR in persons with eGFR at regimen initiation < 60/ml/min/1.73m^2)
- o NADM (excluding hepatocellular carcinoma)

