#### AIM 1. Describe PLWH initiating CAB+RPV LA regimen

Baseline characteristics including demographics, clinical, immunological and virological characteristics at baseline (i.e. at initiation of regimen) will be described using the following descriptive statistics: n (non-missing sample size), median, 1st quartile, and 3rd quartile. The frequency and percentages (based on the non-missing sample size) of observed levels will be reported for all categorical variables.

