## Comorbidities

Has the subject experienced any of the comorbidities listed below?	○ No No Yes		
HCV co-infection	○ No ○ Yes		
Is date of HCV diagnosis known?	○ No MHHCV_DTYN ○ Yes		
Date of HCV diagnosis	MHHCV_DT	Estimated number of years since HCV diagnosis	MHHCV_YR
HBV co-infection	○ No No Yes		
Is date of HBV diagnosis known?	○ No		
Date of HBV diagnosis	MHHBV_DT	Estimated number of years since HBV diagnosis	MHHBV_YR
ESLD (hepatocellular carcinoma, ascites, hepatorenal grade III/IV hepatic encephalopathy, unspecified oesophageal variceal bleeding, spontaneous baliver transplantation)	Hiver decompensation,	○ No ○ Yes	MHESLD
Please specify condition		MHESLD_SP	
Is date of ESLD diagnosis known?	○ No		
Is date of ESLD diagnosis known?  Date of ESLD diagnosis	○ No	Estimated number of years since ESLD diagnosis	MHESLD_YR
	○ Yes	Estimated number of years since ESLD diagnosis	MHESLD_YR
Date of ESLD diagnosis  CVD (myocardial infarction, stroke,	Yes  MHESLD_DT	Estimated number of years since ESLD diagnosis	MHESLD_YR
Date of ESLD diagnosis  CVD  (myocardial infarction, stroke, invasive coronary procedure)	Yes  MHESLD_DT	since ESLD diagnosis	MHESLD_YR
Date of ESLD diagnosis  CVD (myocardial infarction, stroke, invasive coronary procedure)  Please specify condition	Yes  MHESLD_DT  No Yes  No No Yes	since ESLD diagnosis	MHESLD_YR  MHCVD_YR

ID	CODE	NAME	EXP.CODE	TYPE	FMT/LEN	DERIVATION	CAT. VALUES
1	20R1ID D	Subject ID	20R1ID D	Text	10	R2F:DEMOG:20R1ID	
2	MHYN	Has the subject experienced any of the comorbiditi	MHYN	Category	3		N=No Y=Yes
3	MHHCV	HCV co-infection	MHHCV	Category	3		N=No Y=Yes
4	MHHCV_DTYN	Is date of HCV diagnosis known?	MHHCV_DTYN	Category	3		N=No Y=Yes
5	MHHCV_DT	Date of HCV diagnosi	MHHCV_DT	Date/Time	dd/mm/yyyy		
5	MHHCV_YR	Estimated number of years since HCV diagnosis	MHHCV_YR	Integer	#9		
/	MHHBV	HBV co-infection	MHHBV	Category	3		N=No Y=Yes
8	MHHBV_DTYN	Is date of HBV diagnosis known?	MHHBV_DTYN	Category	3		N=No Y=Yes
9	MHHBV_DT	Date of HBV diagnosi		Date/Time	dd/mm/yyyy		
10	MHHBV_YR	Estimated number of years since HBV diagnosis		Integer	#9		
11	MHESLD	ESLD	MHESLD	Category	3		N=No Y=Yes
12	MHESLD_SP	Please specify condition	MHESLD_SP	Category	35		See Appendix
13	MHESLD_DTYN	Is date of ESLD diagnosis known?	MHESLD_DTYN	Category	3		N=No Y=Yes
14	MHESLD_YR	Estimated number of years since ESLD diagnosis	MHESLD_YR	Integer	#9		
15	MHESLD_DT	Date of ESLD diagnosis	MHESLD_DT	Date/Time	dd/mm/yyyy		

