16	MHCVD	CVD	MHCVD	Category	3		N=No Y=Yes
17	MHCVD_SP	Please specify condition	MHCVD_SP	Category	27		1=Myocardial infarction 2=Stroke 3=Invasive coronary procedure
18	MHCVD_DTYN	Is date of CVD diagnosis known?	MHCVD_DTYN	Category	3		N=No Y=Yes
19	MHCVD_DT	Date of CVD diagnosi	MHCVD_DT	Date/Time	dd/mm/yyyy		
20	MHCVD_YR	Estimated number of years since CVD diagnosis		Integer	#9		
21	MHCKD	CKD	MHCKD	Category	3		N=No Y=Yes

	eForm Code: MH e	Form Title: Comorbidities - Lay	rout	
Please specify condition	MHCKD_SP			
Is date of CKD diagnosis known?	○ No ○ Yes			
Date of CKD diagnosis	MHCKD_DT	Estimated number of years since CKD diagnosis	MHCKD_YR	
NADM (excluding hepatocellular carcinoma)	○ No ○ Yes	М		
Please specify condition	MHNADM_SF			
Is date of NADM diagnosis known?	○ No ○ Yes	YN		
Date of NADM diagnosis	MHNADM_DT	Estimated number of years since NADM diagnosis	MHNADM_YR	
For Office Use Only				
Data Review Reason  CRREAS	Review Date	e Notes for Next Review CRNOT		

ID	CODE	NAME	EXP.CODE	TYPE	FMT/LEN	DERIVATION	CAT. VALUES				
22	MHCKD_SP	Please specify condition	MHCKD_SP	Text	100						
23	MHCKD_DTYN	Is date of CKD diagnosis known?	MHCKD_DTYN	Category	3		N=No Y=Yes				
24	MHCKD_D1	Date of CKD diagnosi	MHCKD_DT	Date/Time	dd/mm/yyyy						
25	MHCKD_YR	Estimated number of years since CKD diagnosis	_	Integer	#9						
26	MHNADM	NADM	MHNADM	Category	3		N=No Y=Yes				
27	MHNADM_SP	Please specify condition	MHNADM_SP	Text	100						
28	MHNADM_DTYN	Is date of NADM diagnosis known?	MHNADM_DTYN	Category	3		N=No Y=Yes				
29	MHNADM_DT	Date of NADM diagnosis	MHNADM_DT	Date/Time	dd/mm/yyyy						
30	MHNADM_YR	Estimated number of years since NADM diagnosis	MHNADM_YR	Integer	#9						
Repea	Repeating Question Group: , Borders: Yes, RowStatus: Yes, RowNumbers: Yes, DisplayRows: 3, InitialRows: 1, Min Repeats: 1, Max Repeats: 20, Main Row Type: Single-Line, Sub Row Type: Multi-Line										
31	CRREAS	Data Review Reason	CRREAS	Category	36, Optional		See Appendix				
32	CRDAT	Review Date	CRDAT	Date/Time	dd/mm/yyyy, Optional						
33	CRNOT	Notes for Next Review	CRNOT	Text	500, Optional						

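### CKD is listed as a baseline covariate but defined as a renal event after regimen initiation, which conflicts with the baseline CRF item (minor, separate: the derived BMI field has a units error)

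*Protocol*

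**What the plan says.** Section 8.3.3 opens by stating the role of its variables: "The study will examine the effect of the following potential confounders and effect modifiers on the risk for outcomes of interest". CKD appears there under Comorbidities, after the blocks of variables headed as measured at regimen initiation. Its definition has two arms. The first is a confirmed eGFR below 60, with values more than three months apart, "in persons with eGFR at regimen initiation ≥60/ml/min/1.73m" squared. The second is a "confirmed 25% decline in eGFR in persons with eGFR at regimen initiation" below 60.

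Two analyses use this variable. Under Aim 1 in section 8.7, "characteristics at baseline (i.e. at initiation of regimen) will be described". The risk-factor part of section 8.7 says "All variables described at section 8.3.3 will be assessed", with Cox models for virologic failure, non-adherence and discontinuation, and logistic regression for resistance.

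Annex 1 collects CKD differently. The Comorbidities form is in the Baseline column of the visit grid and asks "Has the subject experienced any of the comorbidities listed below". For CKD it then takes Yes or No, a free-text condition, the question "Is date of CKD diagnosis known", and either a date or an estimate of the years since diagnosis.

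BMI is named in section 8.3.3 only as "Body Mass Index (BMI), height, weight", without a formula. The Regimen Initiation form collects height in centimetres and weight in kilograms, has an entered BMI field, and derives a further field, BMI_D, as `WKG/(HCM*HCM)` in integer format.

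**The concern.** A baseline covariate should record a state that exists at time zero. The CKD rule takes the initiation eGFR as its reference point and asks whether kidney function then moved, which is how an incident outcome is defined. Two consequences follow if the rule is applied as written. People with established, stable reduced function, whom a CKD covariate is meant to identify, are placed in the unaffected group. People become positive through events after the Cox clock has started. Positive coding then also requires staying under observation for more than three months, because confirmation needs two values that far apart.

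The protocol and its own CRF also give sites two different rules for the same item. If sites differ in which one they follow, the variable has no single meaning, and the supplied CRF holds nothing from which to rebuild it.

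**Working it through.** **CKD: the rule evaluated as written**

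Inputs are the two arms in section 8.3.3. Let e0 be eGFR at initiation.
- If e0 ≥ 60, CKD requires a confirmed eGFR < 60.
- If e0 < 60, CKD requires a confirmed fall of 25%, i.e. to 0.75 × e0 or lower.

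The e0 values below are illustrative, because the protocol gives no eGFR distribution.

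| eGFR at initiation | CKD if eGFR stays unchanged? | Later value needed |
|---|---|---|
| 95 | No | below 60 |
| 62 | No | below 60 |
| 59 | No | 0.75 × 59 = 44.25 or lower |
| 45 | No | 0.75 × 45 = 33.75 or lower |
| 30 | No | 0.75 × 30 = 22.5 or lower |
| 20 | No | 0.75 × 20 = 15 or lower |

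No initiation value is enough to qualify. The rule can also reverse the order of patients: someone who starts at 62 and is later confirmed at 59 (a fall of 3) is CKD, while someone stable at 30 is not.

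The wording could be stretched to mean a decline before initiation. A person now at 45 would then qualify only after an earlier value of at least 45/0.75 = 60. Stable function at 45 is still missed.

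**CKD: protocol and CRF side by side**

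| | Section 8.3.3 | Annex 1, Comorbidities form |
|---|---|---|
| Basis | eGFR change relative to initiation | history, Yes/No |
| Timing | after initiation, on the natural reading | diagnosis date or years since diagnosis |
| Stable eGFR 45, diagnosed years ago | not CKD | Yes, if answered by diagnosis |
| eGFR data | needed | no eGFR or creatinine field on any supplied form |

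Section 8.5 says biochemistry parameters will be collected, but no supplied form has a place for eGFR or creatinine.

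**BMI_D**

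Inputs are WKG in kg, HCM in cm, and storage as an integer. Body sizes are illustrative.

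| Weight, height | As printed: WKG/(HCM × HCM) | Stored | With height in metres |
|---|---|---|---|
| 80 kg, 180 cm | 80/32,400 = 0.0025 | 0 | 80/1.80² = 24.7 |
| 70 kg, 175 cm | 70/30,625 = 0.0023 | 0 | 70/1.75² = 22.9 |
| 250 kg, 140 cm | 250/19,600 = 0.0128 | 0 | 250/1.40² = 127.6 |

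The printed formula is too small by 100² = 10,000. At 175 cm, a weight of 0.5 × 175² = 15,312.5 kg would be needed to reach even 0.5. BMI_D is therefore 0 for every real participant, by rounding or truncation.

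**The case against.** The strongest reply on CKD is that sites complete the form and do not work from section 8.3.3. A question about years since diagnosis only makes sense for a pre-existing condition, so a site would reasonably record established CKD as Yes. The text of the CKD question itself is missing from the extracted form layout, so it cannot be shown that sites are told to use the 8.3.3 rule. This stands, and it limits the claim. A reader might infer that everyone with eGFR below 60 at initiation will be recorded as free of CKD. The documents do not support that: they show two conflicting rules, not which one sites follow.

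It is also fair that CKD is one candidate among many, carried into the multivariable model only if its univariable P is below 0.20, in a study that tests no formal hypothesis. A reader might infer that the Cox models are biased by a known amount. No CKD prevalence or effect is given, so neither direction nor size can be stated.

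On BMI, a reader might infer that the study cannot obtain a valid BMI. That is wrong. Section 8.3.3 attaches no formula to BMI, an entered BMI field exists, height and weight are stored, and nothing names BMI_D as the analysis variable. Neighbouring cells of the annex table are visibly damaged in the text available, so a lost scaling factor cannot be excluded.

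The objection does not remove the defect in the CKD definition. It is wrong for a baseline covariate on either reading, and a later analysis plan could restate it but could not recover eGFR values that the CRF does not hold.

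**Conclusion.** The CKD definition in section 8.3.3 is wrong for its stated use and conflicts with the CRF item that collects it. If it is followed, stable reduced kidney function counts as no CKD, and follow-up events enter a covariate used for the baseline description and the factor models. The number affected is unknown. It ranges from none, if every site answers by diagnosis, to all participants with stable eGFR below 60 at initiation, if every site applies the written rule. The estimates of virologic failure, discontinuation, adherence and resistance, and the precision tables in section 8.4, do not depend on it. The point should be corrected, but it does not threaten the main results.

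The BMI_D error is minor and separate. The field carries no information as printed, but does harm only if it is used unchecked.

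Both conclusions rest on the supplied text of the protocol and Annex 1. The live eCRF may differ.

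**What to change.** 1. In section 8.3.3, define CKD by status at or before regimen initiation, for example eGFR below 60 ml/min/1.73m² confirmed more than three months apart. Print the same definition beside the CKD question on the Comorbidities form.
2. Keep the present wording only if incident CKD is wanted as a follow-up outcome. In that case, move it out of the covariate list and add eGFR with dates to the CRF.
3. Check the BMI_D derivation in the live eCRF. If it is as printed, change it to `WKG/((HCM/100)*(HCM/100))` with one decimal and recalculate stored values. Otherwise, drop BMI_D and use the entered BMI, or compute it from stored height and weight.

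The cost is one definition line, one form label and one formula with its format. Items 1 and 3 need no new tests, since eGFR is read from the existing medical record. The CKD change is best made before baseline forms are completed. For forms already completed, sites would have to confirm the CKD answer against the record, because the supplied CRF holds no eGFR to check it.
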